5.1.2. Pooling Sites for Analysis

Data from all investigational sites will be pooled for the analysis, and no separate analysis by site will be performed.

5.1.3. Handling of Missing Data

No imputation due to missing data will be applied.

For the analysis datasets of AEs and concomitant medications/procedures, if the start/stop date of an AE/concomitant medication is missing or partial, the corresponding study day will be left blank. However, inferences will be made from the partial and missing dates to classify medications as prior and/or concomitant and AEs as treatment emergent or not treatment emergent. These inferences are described in Section 6.4 and Section 9.1, respectively.

5.2. Data Summaries

5.2.1. Continuous Variables

Continuous variables will be summarized using descriptive statistics including the number of non-missing values (n), mean, standard deviation (SD), median, minimum, and maximum. Where specified in the table shells, the 25th and 75th percentiles will also be provided.

Pharmacokinetic parameters will also be summarized using the geometric mean and percent coefficient of variation (%CV).

Means (arithmetic and geometric), medians, confidence intervals, and 25th and 75th percentiles will be presented to one decimal place beyond that with which the data was captured. Standard deviations will be presented to two decimal places beyond that with which the data was captured. Minimum and maximum will be displayed to the same number of decimal places as that with which the data was captured. %CV will be displayed to one decimal place for all PK parameters.

5.2.2. Categorical Variables

Categorical variables will be summarized by counts and percentages. All percentages will be rounded to one decimal place. The percentage will be suppressed when the count is zero.

Unless otherwise specified, the denominator for all percentages will be the overall number of subjects (or other experimental unit, eg bleeding episodes) with non-missing data for a given summarization.

6. STUDY POPULATION

6.1. Disposition of Subjects

Subject disposition will be summarized for each dose level and overall using the All-Enrolled Analysis Set. The table will present the number and percentage of subjects in the Safety Analysis Set and the PK Analysis Set. In addition, the number of subjects who completed the study and the number of subjects who discontinued from the study early, including the primary reason for discontinuation, will be tabulated.

Subject disposition, including date of last visit and reason for early discontinuation, for subjects who did not complete the study, will be provided in a listing.

6.2. Demographic and Baseline Disease Characteristics

6.2.1. Demographics

Demographics will be summarized by dose level and overall using the Safety Analysis Set.

Demographic characteristics will include age, height, weight, and body mass index (BMI) at screening plus race, ethnicity, and country. Age will be summarized both as a continuous variable using descriptive statistics and categorically (<18, 18-24, 25-34, 35-44, 45-54, 55-64, \geq 65 years). Height, weight, and BMI will be summarized using descriptive statistics where BMI is calculated as weight (kg) / height (m²). Race, ethnicity, and country (United States, Japan) will be summarized categorically by number and percentage of subjects.

Demographics will also be presented in a listing using the All-Enrolled Analysis Set.

6.2.2. General Medical and Surgical History

Medical and surgical history will be recorded at screening. The number and percentage of subjects with any medical and surgical history will be summarized for each body system overall and by dose level using the Safety Analysis Set. A patient will be counted only once if the patient reported one or more occurrences of the same body system.

Medical and surgical history, including specific details, will also be presented in a listing using the All-Enrolled Analysis Set.

6.2.3. Hemophilia History

Hemophilia medical and bleeding history will be reported at screening and will be summarized by dose level and overall for the Safety Analysis Set.

Categorical summaries will be provided for lowest documented historical FVIII level (<1%, \geq 1%), family inhibitor history, human immunodeficiency virus (HIV) status, Hepatitis C (HCV) status, Hepatitis B (HBV) status, blood type, [REDACTED], Rh factor, vaccination history, and types of FVIII product previously administered at study entry.

Time since diagnosis of hemophilia, number of bleeds in the past 3 months and typical dosing for treatment of bleeds (minor, moderate, major) will be summarized with descriptive statistics.

In addition, a summary of the most recent pre-study FVIII regimen and other prior FVIII regimens used in the past 3 months will be provided including categories for most recent pre-study FVIII regimen (prophylaxis, on-demand), time on pre-study regimen (>12 months, 6-12 months, < 6 months), and the frequency of injections for those subjects who indicated prophylaxis as their most recent pre-study regimen.

Hemophilia medical and bleeding history will also be presented in listings using the All-Enrolled Analysis Set.

6.3. Protocol Deviations

All protocol deviations will be recorded throughout the study. The overall number of subjects with major protocol deviations will be summarized by category using the Safety Analysis Set.

Protocol deviations will also be presented in listings using the All-Enrolled Analysis Set.

6.4. Non-study Drug Medications

6.4.1. Prior and Concomitant Medications

Prior medications include all medications taken within 30 days prior to the administration of the first dose of Advate.

A concomitant medication is any drug or substance administered from Day 1 of the study through the last study visit. Medications with missing start dates will be assumed to be concomitant, unless the stop date is before the Advate dosing date.

Data on both prior and concomitant medications will be summarized by dose level and overall for the Safety Analysis Set. In addition, prior and concomitant medications will also be presented in data listings for the All-Enrolled Analysis Set. In these listings, medications taken during a major surgical period will be flagged.

Number of days from study drug administration (both for Advate and BIVV001) to the start date of the medication will be included and calculated using the following formula:

If medication start date is on or after study drug administration, days from study drug administration = medication start date – study drug administration date + 1. If medication start date is before study drug administration, days from study drug administration = medication start date – study drug administration date.

Number of days from study drug administration to the stop date of prior or concomitant medication will be calculated similarly.

If start or stop dates are incomplete or missing, then the number of days from study drug administration to the start/stop date will be reported as missing – no imputation of dates will be performed.

6.4.2. Other Therapies and Procedures

Other therapies and procedures will be displayed in a data listing for the All-Enrolled Analysis Set. The listing will include therapy or procedure name, start date, end date, reason for therapy

or procedure and whether the procedure was considered surgical and the surgery category (minor/major).

6.5. Study Drug

Study drug administration for both Advate and BIVV001 will be listed using the Safety Analysis Set. This includes the study drug administered, lot number, nominal IU amount administered per vial, actual IU amount administered per vial, number of vials injected, total actual IU injected, total volume injected, and infusion start and stop dates and times.

6.6. Bleeding Episodes

As this is a safety and PK study, the doses of Advate and BIVV001 being administered are not intended to provide the subject optimal protection from new bleeding episodes. Bleeding episodes will be collected during the study including date and time of bleeding episodes, location of bleed, type of bleed, and treatment for bleed. If bleed is treated with FVIII infusion, the date and time of infusion will be collected.

Bleeding episodes will be presented by dose level and subject in a data listing.

7. EFFICACY ANALYSES

No efficacy analyses are planned for this study. However, the PK evaluation will provide an initial understanding of the efficacy of BIVV001 in humans, consistent with the view from the European Medicines Agency (EMA) guidelines that PK data are considered the most important surrogate markers for efficacy of a new FVIII product.

8. PHARMACOKINETIC ANALYSES

All PK analyses will be performed based on the PK analysis set (PKAS). The detailed methodology and software used will be documented in the PK report.

8.1. Summary of FVIII Activity

For Advate (FVIII) treatment, FVIII activity (one-stage clotting and chromogenic assays) will be assessed at screening, just prior to the administration of Advate (pre- dose of 25 IU/kg or 65 IU/kg) at 0.5, 1, 6, 24, 48, and 72 hours post-injection.

For BIVV001 treatment, FVIII activity (one-stage clotting and chromogenic assays) will be assessed just prior to the administration of BIVV001 and at 0.17, 0.5, 1, 3, 6, 9, 24, 48, 72, 96, 120, 168, and 240 hours (10 days) post injection for subjects administered the low dose of BIVV001 and additionally at 288 and 336 hours (14 days) post injection for those subjects administered the high dose of BIVV001 and at the End of Study/Early Termination Visit.

Hours from treatment will be calculated as the time elapsed from initiation of the Advate injection to sample collection for the Screening period and Advate treatment period or as the time elapsed from initiation of the BIVV001 injection to sample collection for the BIVV001 treatment period.

FVIII activity will be summarized by study drug, dose level, visit, and by one-stage clotting assay and two-stage chromogenic assay, respectively and presented in one data listing for each study drug for the Safety Analysis Set. Summary descriptive statistics will include the number of non-missing values, mean, geometric mean, standard deviation, percent coefficient of variation, minimum, and maximum.

FVIII activity versus time profiles will be plotted in both original and log scale for each subject by study drug for both assays. In addition, the mean FVIII activity versus time profiles at each dose level will be constructed for the two study drugs in the original and log scale for both assays.

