2.1.2. Secondary Objective(s)

The secondary objective of the study is to characterize the PK of BIVV001 after a single IV administration compared with the PK of Advate, with FVIII activity measured by the one-stage (activated partial thromboplastin time [aPTT]-based) clotting assay.

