3. STUDY DESIGN

3.1. Overall Study Design

[figure not shown]
This is a Phase 1/2a, open-label, dose-escalation, multicenter study designed to evaluate the safety, tolerability, and PK of a single IV dose of BIVV001 in subjects with severe hemophilia A who have received at least 150 exposure days of prior FVIII treatment.

Approximately 18 male PTPs aged 18 to 65 years will be enrolled: approximately 8 subjects in the low-dose cohort (Advate 25 IU/kg and BIVV001 25 IU/kg) and approximately 10 subjects in a high-dose cohort (Advate 65 IU/kg and BIVV001 65 IU/kg).

Each subject will be dosed with Advate followed by a PK sampling period. Following a brief washout period, each subject will then be administered BIVV001 followed by a PK sampling period. Subjects will undergo safety observation for 28 days following the injection of BIVV001, including sample collection for inhibitor assessments 14 and 28 days after the injection of BIVV001. Subjects may resume treatment with their pre-study FVIII product during the 28-day observation period after completing Visit 14 activities (which include the 14-day inhibitor test). Only subjects with adequate samples for PK and inhibitor characterization following both Advate and BIVV001 dosing will be considered evaluable; additional subjects will be enrolled as needed to ensure that at least 6 subjects in the low-dose cohort and 8 subjects in the high-dose cohort provide evaluable PK and inhibitor data.

An independent Data Safety Monitoring Committee (DSMC) will evaluate the safety data from the study on an ongoing basis.

Figure 1: Study Schema

* Screening may be extended up to 120 days with prior Sponsor approval. If the Screening Period extends beyond 56 days, screening assessments must be repeated as specified in the protocol prior to dosing with Advate. Washout duration at least 96 hours (4 days) from the most recent FVIII dose (prestudy FVIII) for a conventional product, 120 hours (5 days) for an extended half-life FVIII product.

[figure not shown]
** Washout duration at least 72 hours (3 days) from the Advate dose for the BIVV001 low-dose cohort, and at least 96 hours (4 days) for the BIVV001 high-dose cohort.

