9.2. Clinical Laboratory Evaluations

The following protocol required laboratory tests will be performed:

- Hematology: red blood cell count, white blood cell count and differential, platelet count, hemoglobin, and hematocrit
- Clinical chemistry: ALT; AST; alkaline phosphatase; gamma-glutamyl transferase; bilirubin; blood urea nitrogen; creatinine; glucose; total protein; sodium; potassium; and chloride

- Urinalysis: specific gravity; pH; color; appearance; leukocyte esterase; protein; glucose; ketones; occult blood; bilirubin; urobilinogen; nitrite; and microscopic examination of urine sediment
- Coagulation and thrombosis markers: prothrombin time (PT); aPTT; d-dimer; international normalized ratio; thrombin anti thrombin complex; prothrombin fragment 1.2; and the von Willebrand comprehensive panel (which includes assessments of FVIII activity, VWF ristocetin cofactor activity, and VWF antigen)
- [REDACTED]
- [REDACTED]
- Detection of FVIII inhibitors, as determined by the Nijmegen modified Bethesda assay. A subject's blood will be considered to be positive for FVIII inhibitor when an initial test result of ≥ 0.6 BU/mL is identified and confirmed by a subsequent test result from an independent blood sample collected within 2 to 4 weeks of the first positive sample.

Refer to Section 5 of the protocol for the timing of assessments.

Laboratory assessments taken during the surgery period will be listed only and will not be included in the laboratory data summaries.

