9.2.3. Coagulation Parameters

Samples for coagulation parameters (PT, aPTT, D-dimer, international normalized ratio, thrombin-anti-thrombin, and prothrombin fragment 1.2, and vWF) will be collected at Screening, Visits 2 and 3 (pre-injection for Advate and 1, 6, and 24 hours post-injection), Visits 6 and 7 (pre-injection for BIVV001 and 1, 6, and 24 hours post-injection), Visit 14 (14 days post-injection for BIVV001), and at the End of Study/Early Termination Visit.

Hours from treatment will be calculated as the time elapsed from initiation of the Advate injection to sample collection for the Screening period and Advate treatment period or as the time elapsed from initiation of the BIVV001 injection to sample collection for the BIVV001 treatment period.

Coagulation data and change from baseline will be summarized over time using descriptive statistics for each drug and dose level group using the Safety Analysis Set. The data will also be presented in a data listing using the Safety Analysis Set.

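### End of Study FVIII activity and aPTT are tabulated under BIVV001 even when the subject is back on another FVIII product

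*SAP*

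**What the plan says.** **FVIII activity.** SAP Section 8.1 lists the BIVV001 sampling times and closes the list with "and at the End of Study/Early Termination Visit". It then states that "FVIII activity will be summarized by study drug, dose level, visit, and by one-stage clotting assay and two-stage chromogenic assay, respectively". The sentence could be read as giving the End of Study sample to the high-dose cohort only; the point is the same on either reading.

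**Coagulation.** Section 9.2.3 also samples at "Visit 14 (14 days post-injection for BIVV001), and at the End of Study/Early Termination Visit", and says that "Coagulation data and change from baseline will be summarized over time using descriptive statistics for each drug and dose level group". The parameters include aPTT and vWF. Section 9.2 describes the vWF test as the "von Willebrand comprehensive panel (which includes assessments of FVIII activity, VWF ristocetin cofactor activity, and VWF antigen").

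**Return to pre-study FVIII.** Sections 3.1, 5.1.1.5 and 9.1 allow it once Visit 14 is complete. Section 5.1.1.5 runs the BIVV001 period on to the 28-day visit. Section 5.1.1.6 defines a separate period that begins with the first dose of the pre-study product, but only the adverse event summaries in Sections 9.1 and 9.1.2 use it.

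**Exclusions of values.** Unscheduled visits are left out of summaries (Sections 5.1 and 5.1.1.10). For surgery, Section 9.2 says: "Laboratory assessments taken during the surgery period will be listed only and will not be included in the laboratory data summaries". Nothing comparable covers values drawn after non-study FVIII.

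**The concern.** The secondary objective in Section 2.1.2 rests on "FVIII activity measured by the one-stage (activated partial thromboplastin time [aPTT]-based) clotting assay". The SAP describes nothing in this assay that separates BIVV001 from a subject's own FVIII product. The SAP recognises the problem at the start of the study: Section 3.1 requires a washout before Advate of at least 96 hours "for a conventional product, 120 hours (5 days) for an extended half-life FVIII product". It sets no such condition for using the End of Study value.

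These subjects have endogenous FVIII below 1 IU/dL (Section 1). A mean of several IU/dL in a BIVV001 row at the 28-day visit could be read as activity persisting from the single dose. The aPTT has a similar problem. Its baseline (Section 5.1.1.9) is the last value before the first study drug dose, and so follows the washout, whereas the End of Study value may not. Section 7 treats PK as the first indication of efficacy, so the misreading would matter to a reader of these tables.

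**Working it through.** **1. Does any rule in the SAP reach these values?**

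| Rule | Section | Reaches End of Study values after resumption? |
|---|---|---|
| Unscheduled visits excluded | 5.1, 5.1.1.10 | No. End of Study is a scheduled visit |
| Data tabulated at the eCRF visit | 5.1.1.10 | Keeps them in the End of Study row |
| Surgery-period results listed only | 9.2 | No, unless surgery took place |
| PK Analysis Set | 4.3 | No. It selects subjects, not values |
| Period of pre-study FVIII use | 5.1.1.6 | Defined, but applied only to adverse events |

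Scheduled profile samples end at 240 h (low dose) or 336 h (high dose), that is 10 or 14 days, before resumption is permitted. Those rows are affected only in a subject given FVIII for a bleed, which is not quantified here.

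**2. Activity from the non-study product.** The SAP states no figure to reproduce. The inputs are assumptions: recovery 2 IU/dL per IU/kg; low end 25 IU/kg with a 10 h half-life; high end 50 IU/kg with a 19 h half-life, to include extended half-life products.

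Level = 2 × dose × 0.5^(hours / half-life)

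| Hours since last dose | Low end (IU/dL) | High end (IU/dL) |
|---|---|---|
| 24 | 50 × 0.5^2.4 = 9.47 | 100 × 0.5^(24/19) = 41.66 |
| 48 | 1.79 | 17.36 |
| 72 | 0.34 | 7.23 |
| 96 | 0.064 | 3.01 |
| 120 | 0.012 | 1.26 |

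Time to fall to 1 IU/dL: 10 × log2(50) = 56.4 h at the low end and 19 × log2(100) = 126.2 h at the high end.

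**3. Activity left from BIVV001 at 28 × 24 = 672 h.** Same recovery, assumed half-life 40 to 60 h.

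- 65 IU/kg: 130 × 0.5^(672/40) = 0.0011; 130 × 0.5^(672/60) = 0.055 IU/dL.
- 25 IU/kg: 50 × 0.5^(672/40) = 0.0004; 50 × 0.5^(672/60) = 0.021 IU/dL.

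With a wider assumption (peak 200 IU/dL, half-life 72 h) the residue is 200 × 0.5^(672/72) = 0.31 IU/dL, still below 1.

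**4. Amount added to the End of Study arithmetic mean** = share of subjects recently dosed × level (IU/dL).

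| Share | Dosed 24 h before | 48 h before | 96 h before |
|---|---|---|---|
| 10% | 0.9 to 4.2 | 0.2 to 1.7 | 0.01 to 0.3 |
| 25% | 2.4 to 10.4 | 0.4 to 4.3 | 0.02 to 0.8 |
| 50% | 4.7 to 20.8 | 0.9 to 8.7 | 0.03 to 1.5 |
| 100% | 9.5 to 41.7 | 1.8 to 17.4 | 0.06 to 3.0 |

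One subject dosed 24 h before the sample adds 0.9 to 4.2 in a cohort of 10, and 9.47/8 = 1.2 to 41.66/8 = 5.2 in a cohort of 8.

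**5. Arithmetic against geometric mean.** Section 8.1 reports both. As an illustration, put subjects who did not resume at 0.5 IU/dL and those who did at 5 to 50 IU/dL, in a cohort of 8.

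| Resumed | Arithmetic mean | Geometric mean |
|---|---|---|
| 0 of 8 | 0.5 | 0.5 |
| 1 of 8 | 1.06 to 6.69 | 0.67 to 0.89 |
| 4 of 8 | 2.75 to 25.25 | 1.58 to 5.0 |

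**The case against.** - **The protocol may control when the sample is drawn.** Section 9.2 refers to the protocol for the timing of assessments, and the protocol is not at hand. It may require an interval since the last FVIII dose. This would shrink the effect but need not remove it: at 96 h the range is still 0.06 to 3.0 IU/dL per resumed subject.
- **The tables would give signs of mixing.** Section 8.1 asks for the maximum, %CV and individual plots, and a rise after the last profile sample is not what a single dose produces. With one resumed subject of 8, the geometric mean stays below 1 in the illustration. This is fair, but such signs do not tell the reader which product caused the value. If most subjects resumed, the geometric mean moves as well.
- **The size rests on assumptions.** True. The calculation shows what is possible, from nil upwards, not what will occur. The aPTT effect is not quantified.
- **The adverse event rule is not a model for exclusion.** Correct. Section 9.1 keeps those events in the BIVV001 summaries and adds a separate one. It supports the separate summary, while the surgery rule in Section 9.2 is the precedent for leaving values out.
- **The panel's FVIII result may not be tabulated.** Section 9.2.3 names only vWF, so a summary of the panel's FVIII activity is inferred from Section 9.2. The points on Section 8.1 and aPTT do not depend on it.

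**Conclusion.** The concern holds, as a minor one. Followed as written, the SAP places values that may come from another FVIII product in rows labelled BIVV001, and none of its exclusions prevents this. The textual gap is certain. The distortion depends on how many subjects resumed and how long before the visit they were last dosed, neither of which the SAP gives. Under the stated assumptions, a subject dosed 24 to 48 h before the sample contributes 1.8 to 41.7 IU/dL, against under 0.06 IU/dL left from BIVV001, so even one such subject can dominate the arithmetic mean. If nobody resumed, nothing changes. The effect is confined to descriptive End of Study rows and to any profile point plotted at that visit. No effect is claimed on the Section 8.2 parameters, the escalation conditions or the primary endpoints.

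**What to change.** Add to Section 8.1, with a cross-reference in Section 9.2.3 for End of Study aPTT and for the FVIII activity in the von Willebrand panel:

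> Values drawn after the first non-study FVIII dose following BIVV001 (the Section 5.1.1.6 period, or an infusion for a bleed recorded under Section 6.6) will be flagged in the listings and kept out of the BIVV001 by-visit rows and mean profiles. They will be summarised in a separate row labelled as after non-study FVIII, and their number given by time point and dose level. Where only the date of the non-study dose is recorded, a value from the same day is treated as drawn after it unless the order is documented.

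Flagging the values and leaving them out, without the separate row, would also serve. A rule by value is better than dropping the visit, because early-termination samples taken before any resumption remain usable.

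**Cost.** SAP wording and one derived flag, using a date that Section 5.1.1.6 already needs. The same-day rule is there because infusion times are described only for bleed treatment (Section 6.6), while Section 6.4.1 counts medication timing in days. Some values that have already washed out will also be set aside, late time points will have fewer subjects, and selection is possible because subjects treated for bleeds may differ. The separate row and the counts make this visible.
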